### **Potential benefits of the proposed research to the subjects and others**

The potential benefits to women participating in this study include close monitoring of participants' alcohol and drug use as well as participants' increased awareness of community resources for IPV and alcohol and drug-related issues. Half of the participants in this study will not receive any form of an "active" intervention, and thus are unlikely to receive any direct health benefit; however, women in both conditions will receive a list of local substance use treatment referrals and community resources. Half of the participants will receive a brief intervention designed to increase the likelihood of reductions in substance use and IPV, self-change and/or obtaining community resources for alcohol and drug use.

We believe that the risks to participants in this study are very low, particularly given the lack of connection between identifying information and data. We believe that the risks that are present are justified given the tremendous potential of this research to produce a replicable and low-cost motivational intervention that is appropriate for this group. Such an intervention, then, could potentially be presented to unprecedented numbers of persons in a way that is financially

and logistically feasible, potentially leading to beneficial effects for large numbers of substance using women with IPV.

*Importance of the knowledge to be gained.* An exploratory approach towards the development of an effective brief computer-based intervention for sheltered battered women with substance use problems could increase the likelihood of these women accessing services for their substance use difficulties and reducing their substance use and IPV severity. Further, there is promising evidence that the application of brief interventions to substance using women offers substantial benefits to the woman. The paucity of research targeting substance use problems with battered sheltered women and the potential success of implementing a computer-based brief intervention in this population invites the proposed research investigation.

### **Data Analysis:**

For this treatment development grant, assessment of feasibility and acceptability of the intervention and research procedures is the primary goal. Nonetheless, pilot data can be used to demonstrate whether the effects of treatment look promising across a set of outcome variables, to begin to examine distribution of outcome variables and ranges of correlations among variables across time to inform future analytic strategies, and to suggest, in concert with results from larger scale clinical trials in related fields, the range of effect sizes that would be reasonable to expect in a future trial. As a result, we will obtain the between treatment condition effect size estimates at each assessment (e.g., Cohen's *d* or *h*) as well as the correlation between the same dependent variable at adjacent assessments. We anticipate we will have complete data on approximately 41 participants. Sample size guidelines for treatment development from Rounsaville et al. recommend 15 to 30 participants per cell. Given that group means begin to stabilize by around 15, we believe a sample of ~20-21 in each condition should provide some information relevant to demonstrating potential promise for the intervention.

Primary analyses will be *intent-to-treat* (using data from all treatment enrollees). Secondary *completer analyses* (including only subjects who attend at least the computer-based session) will also be conducted. Analysis strategies used (hierarchical linear modeling [HLM]) can accommodate missing data, and can be used in a sample of 41 with a highly constrained covariance structure. Outcome variables may be transformed to improve normality if needed. If any outcome variable is too zero-inflated to be normalized through transformation, it will be analyzed with logistic regression or generalized estimating equation techniques in this small pilot study, and then with zero-inflated Poisson or negative binomial regression techniques in the subsequent fully-powered study. We will compare rates of missing data across conditions. Per recent clinical trials guidelines analyses will adjust for baseline levels of dependent variables but will not test or adjust for any other baseline differences between conditions that result from randomization. Participants' data will be directly exported from CIAS to a database immediately after each participant session. CIAS and ACASI data will be backed up daily and checked once per month for out of range values, missing data, and other quality issues.

Study Feasibility and Intervention Feasibility/Acceptability. One of the primary goals of a treatment development study is to demonstrate the feasibility of the proposed treatment and of the study and recruitment methods. As a result, we will assess the feasibility of the research procedures by examining study recruitment and refusal rates, participants' willingness to be randomized, follow-up rates, and range of responses to study questionnaires. We will assess the feasibility and acceptability of SHE by examining rates of intervention attendance, and rates of intervention completion (both the intervention session and booster session for both conditions). For our rates of session completion, we expect at least 80% will complete both baseline and booster sessions based on our good attendance rates in our other IPV intervention studies. We will also examine reasons for termination for consistent patterns. We will examine the acceptability of both SHE and control conditions using data from *Satisfaction with CIAS Software Scale* (i.e., an average score of 4 out of 5 on the CIAS satisfaction scale; at

least highly satisfied and engaged with software) and CSQ-8-R (i.e., above the average score of 27 on the CSQ-8-R)(see Section C.3.11). We will examine mean, mode, and median scores.

**Other Primary Outcomes.** (1) In addition to examining pre-post changes in the intervention condition, we will calculate the effect size and 95% confidence intervals for number of substance using days [including drug-using and heavy drinking days (4+ standard drinks)]. Exploratory tests for differences between conditions will use HLM, with using days in the 6 months prior to intake as a covariate. (2) **Secondary Outcomes.** We will examine pre-post changes in the intervention condition, and calculate between-groups effect sizes and 95% CIs for (1) total days of treatment received measured by the TSR, and for (2) reduction in IPV severity using the CAS. IPV severity will be operationalized as the sum of the number of abusive acts endorsed on the CAS; a scoring method found to provide a valid measure of abuse severity IPV. For exploratory tests for differences between conditions, we will use HLM with baseline scores as covariates.

**Assessment of processes and individualized treatment response.** This R34 treatment development study is underpowered to explore mediation effects (MacKinnon’s mediation power = 16%); a subsequent R01 will test the hypothesis that improvement in readiness to change and self-efficacy variables partially mediate the effects of SHE on our primary outcomes. Similarly, though a full test of moderation will be conducted in a subsequent R01, we will explore potential predictors of intervention response including IPV severity and baseline substance use severity, and will conduct preliminary examinations of large minority differences in this study.

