IPV: The Composite Abuse Scale (CAS) is a widely used self-report of behaviors scale with 4 subscales that measure severe, combined abuse, emotional abuse, physical abuse, and harassment. The CAS has recently been published in the Centers for Disease Control and Prevention compendium of intimate partner violence measures. It consists of 30 items presented in a six point format requiring respondents to answer “never”, “only once”, “several times”, “monthly”, “weekly” or “daily” in a twelve month period.

The Cyber Stalking Scale measure is a 6 –item measure and assesses the use of technologies in stalking and harassment.

Safety Behavior Checklist (SBC) has 15 items that assess the use of strategies suggested to keep victim safe (e.g., hiding money and extra clothing).

*Theorized Mediators: The Confidence Ladder* will be used to assess the participants’ levels of confidence regarding their ability (self-efficacy) to change and abstain from substances. *Readiness Ruler* will be used to assess the degree to which participants’ are ready to cut down or quit alcohol or drugs.

Women who participated in the SHE intervention will complete a computer-based measure at the 3- and 6-month follow-up assessment to determine the extent to which participants achieved their goals on their personalized plan; an indication of the degree to which the SHE intervention had an impact on behavioral change. This measure will follow a similar format to the Effectiveness in Obtaining Resources Scale, which assesses battered women’s effectiveness in obtaining various resources.

At follow up, if a participant is unable to meet in-person to complete the assessments (e.g. participant has moved out of state), she will be given the option of participating in the assessment over the phone. Phone sessions will consist of the research assistant administering all the follow up assessments listed above via a phone session, with the exception of breathalyzer, urine, and hair sample testing.

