**Retention**

The PI has had high retention rates (+ 85%) in treatment trials involving difficult-to-follow populations (e.g., substance using women with interpersonal violence and women with IPV). Furthermore, our prior research with battered residents leaving shelter, our follow up rates have been 82% retention at 6 months post-shelter and 80% at 9 months post shelter. The current study will employ several approaches that we have found helpful in achieving these low attrition rates, including staff’s strong relationships with participants, efforts to value and appreciate the women’s participation in the study, and frequent personal contact with the women for the duration of the study. Research staff calls women to remind them of their appointments and maintain a list of two other people who will always know where the participant resides. We can contact the women through private message on Facebook via a generic Facebook page of “She A. Smith” with no information about who we are or what we do. [name] has used this retention strategy safely and successfully in a study of women residents of a battered women’s shelter in Ohio. Transportation is provided as deemed necessary to complete assessments. Further, compensation for participants’ time for assessments helps facilitate retention. Finally, Rhode Island’s small size and population stability (residents rarely move out of state) also facilitate participant retention.

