### Phase III Refinement of SHE

Based upon our experience during the Development and Trial Phase, evaluation of the program, and feedback from participants, the Investigator Team will revise the intervention. These revisions and the published qualitative and quantitative results of this study will represent the final products of this R34 and will be used in conjunction with information regarding the recruitment methods and retention of participants in the application for an R01 to evaluate this new intervention for our target population.

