**Intervention for Battered Sheltered Women
With Substance Use Randomized Trial**

NCT #: NCT02629133

December 22, 2017

Statistical Analyses

Statistical Analysis Overview

1. Descriptively characterize the: (a) **feasibility** of the SHE Program, and the (b) **acceptability** via participant report of ease of use, helpfulness, and overall satisfaction.
2. Examine preliminary evidence that relative to control condition, the computer-based intervention (SHE) will result in improvements in our primary outcomes of substance use (heavy drinking or drug using) days over a 6-month postshelter period and in our secondary outcomes of greater use of substance use services (both treatment and self-help utilization) and reduced IPV severity over a 6-month postshelter period. Theorized mediators include readiness to change and self-efficacy for behaviors related to substance use.

Comparison Group Selection

SHE intervention
Control condition

Comments

Assessment of feasibility and acceptability of the intervention and research procedures is the project's primary goal. However, pilot data can be used to demonstrate whether the effects of treatment look promising across a set of outcome variables. We will obtain the between treatment condition effect size estimates at each assessment and the correlation between the same dependent variable at adjacent assessments. A sample of ~20-21 in each condition should provide some information relevant to demonstrating potential promise for the intervention.

Type of Statistical Test [*]

Other (primary analyses focus on feasibility and acceptability)

Comments [*]

Secondary analyses will explore differences between conditions on outcome variables.

Statistical Test of Hypothesis (or Method of Estimation or Other Statistical Analysis required)

We will calculate the effect sizes and 95% confidence intervals for intervention effects on outcomes using hierarchical linear modeling with a tightly constrained covariance structure. However, this is not primarily a hypothesis-testing study.

P-Value [*]

There is no null hypothesis. If we use any p-value, it will be .05.

Comments

None

Method [*]

We will calculate the effect sizes and 95% confidence intervals for intervention effects on outcomes using hierarchical linear modeling with a tightly constrained covariance structure.

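### Does the unexplained step from 60 randomised women to about 41 with complete data need correcting?

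*Protocol*

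**What the plan says.** The protocol's Methods - Randomized Pilot Trial section fixes enrolment at 60 women in two groups. Data Analysis then states "We anticipate we will have complete data on approximately 41 participants", and from this takes roughly 20 to 21 per condition, set against a cited guideline of 15 to 30 per cell. The SAP repeats the per-arm figure in its comments under Comparison Group Selection: "A sample of ~20-21 in each condition should provide some information".

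Two other places give rates that bear on the count:

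- Retention reports rates above 85% in the principal investigator's earlier treatment trials. For women leaving shelter it says "our follow up rates have been 82% retention at 6 months post-shelter".
- Data Analysis says of the sessions that "we expect at least 80% will complete both baseline and booster sessions".

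The same section names two analysis sets. The primary one is intent-to-treat, using all enrollees. The secondary one is a completer set, "including only subjects who attend at least the computer-based session". It adds that the hierarchical linear model copes with missing data and "can be used in a sample of 41 with a highly constrained covariance structure".

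**The concern.** The step from 60 to 41 is not shown, and complete data is not defined. A reader who turns to Retention for the missing rate finds figures that leave 9 to 11 women without follow-up, not 19. If 41 came from combining session completion with retention, the resulting group (both sessions attended and followed up) is neither of the two named analysis sets. Yet 41 is the number cited when the model is said to be usable.

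Three consequences could be feared:

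- The intent-to-treat model might be expected to lose more women than the retention record suggests. Baseline enters as a covariate, so a woman with neither follow-up supplies no outcome to the model.
- The later grant application is to draw on "information regarding the recruitment methods and retention of participants in the application for an R01". An undefined forecast cannot be checked against what is observed. Read as planning rates, the candidates differ: 100 women with complete data would need 146 enrolled at 68.3%, 122 at 82% and 118 at 85%.
- Telephone follow-up covers all assessments "with the exception of breathalyzer, urine, and hair sample testing", so it is open whether a woman followed by telephone counts as complete.

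**Working it through.** **Inputs.** Randomised: 60 (Methods - Randomized Pilot Trial). Stated count: 41 (Data Analysis). Retention: 82% at 6 months after shelter, and 85% or more in other trials (Retention). Completion of both sessions: at least 80% (Data Analysis). The documents give no formula, so the natural candidates are tried in turn.

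**The stated figure.** 41/60 = 68.3%; 60 - 41 = 19 women without complete data; 41/2 = 20.5 per arm, which matches the stated 20 to 21.

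**Candidate derivations.**

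| Meaning of complete | Formula | Count |
|---|---|---|
| Retained, 85% | 60 x 0.85 | 51.0 |
| Retained, 82% | 60 x 0.82 | 49.2 |
| Both sessions and retained, independent | 60 x 0.80 x 0.85 | 40.8 |
| Both sessions and retained, independent | 60 x 0.80 x 0.82 | 39.4 |
| Both follow-ups attended, independent at 82% each | 60 x 0.82 x 0.82 | 40.3 |
| Both sessions and retained, losses never overlapping | 60 x (0.80 + 0.85 - 1) | 39.0 |
| Both sessions and retained, losses never overlapping | 60 x (0.80 + 0.82 - 1) | 37.2 |

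Retention alone does not give 41. Two ordinary readings come within one woman of it (40.8 and 40.3). The second uses 82% for the 3-month visit as well, which is an assumption because no 3-month rate is given. Independence is also an assumption. If the same women tend to miss several things, the counts rise: to at most 48 (60 x 0.80) for the session-based reading, taking 80% at face value, and to at most 49.2 for the two-visit reading. Both the 80% and the 85% are stated as minimums. Working the other way, participants may skip any question (Protection against risk), which lowers a strict complete-data count. On these inputs 41 sits towards the cautious end.

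**Does the spread matter?** The extremes are 37.2/2 = 18.6 and 51/2 = 25.5 per arm, both inside 15 to 30. The approximate 95% confidence half-width for a standardised difference near zero is 1.96 x sqrt(2/n per arm):

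- n = 18.5: 0.64
- n = 20.5: 0.61
- n = 25.5: 0.55
- n = 30: 0.51

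Between 20.5 and 25.5 per arm the half-width changes by 0.06. Over the whole range of candidate counts it changes by 0.64 - 0.55 = 0.09. At any of these sizes the interval is wide and supports the same modest statement about potential promise.

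**The case for a change.** The strongest case for a change is that being able to reach 41 is not the same as explaining it. If the source is 80% x 85%, the count describes women who completed both sessions and were followed up, and missing the booster removes nobody from either named analysis set. If the source is follow-up alone, 41 departs from the Retention section without a reason. Either way a sentence is missing. Follow-up rates are also a listed feasibility measure. Session completion and satisfaction have benchmarks, whereas 41 is the only forward-looking figure on completeness of data.

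The absence of a definition and of a stated rate stands. The rest is weaker:

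- **Mismatch with Retention.** This compares unlike quantities. The sentence on 41 follows a plan to report effect sizes at each assessment and correlations between adjacent ones, which suggests data at all assessments. That count should fall below a retention rate for a single time point.
- **Confusion of analysis sets.** The primary set is named as all enrollees. The remark about 41 says the model can be run at that size; it does not restrict the analysis to those women.
- **Losing 19 women from the model.** This requires complete to mean having any follow-up, which is not its ordinary sense. A woman with one of two follow-ups is incomplete but still contributes. At the Retention rates, women without follow-up number 60 - 51 = 9 to 60 - 49.2 = 10.8.
- **Biological tests.** Measures uses hair and urine results to corroborate self-report, and Data Analysis builds no outcome from them.
- **The later application.** What is carried forward is this study's experience of recruitment and retention. Nothing says the forecast of 41 would be used to size the next trial.

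**Conclusion.** No change is called for. The plan leaves out a definition and an assumed rate, but the figure is not shown to be wrong: the documents' own rates give 40.8 or 40.3 under independence, and neither derivation is confirmed in the text. The spread from 37 to 51 pools different meanings of complete data, and its low end needs losses that never overlap. Even across that whole spread the arms hold about 18 to 26 women, the cited guideline is met, and the approximate confidence half-width moves by about 0.09 of a standard deviation.

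Nothing in the analysis depends on 41. Feasibility and acceptability are primary, the SAP states there is no null hypothesis, and the primary set is all enrollees. The plan already commits to examining follow-up rates and comparing missing data between conditions. Analysts will report the observed counts at each assessment as a matter of course, and those counts are what a later trial would use. Writing down the definition would be tidy, but 41 could stay and no result or conclusion would differ.

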### Methods - Randomized Pilot Trial

Women who are residents of a battered women's shelter (the Women's Center of Rhode Island [WCRI], Sojourner House, New Hope, or Battered Women's Shelter of Summit and Medina Counties), who are at risk substance users within the 3 months prior to entering the shelter as determined by the screener, the NIDA-Modified ASSIST, and endorse IPV within the 3 months prior to entering the shelter as determined by the screener, the WAST (Phase A) will be eligible for the RCT (Phase B). Phase B will use a two-group, randomized, controlled design with 60 shelter residents. After eligible participants consent to participating in the RCT and complete the computer-based baseline assessments the (computer) narrator will "flip a coin" and randomly assign participants to the SHE Program (an initial session plus booster session within three weeks after the initial session) or to the time and attention matched control condition (an initial session plus a booster session within three weeks after the initial session; both consisting of video viewing of popular shows and preference ratings). Next study participants will complete their assigned computer-based intervention. There will be 3- and 6-month post-shelter computer-based follow up assessments (see figure 2 below).

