### **Randomization**

After the screening has been completed (Phase A), for those who are eligible who have provided informed consent, and who have completed baseline assessments, the (computer) narrator "flips a coin" and randomly assigns participants into control vs. SHE Program conditions (Phase B).

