Baseline values of each outcome variable will serve as a covariate in analyses. However, primary results are descriptive results of feasibility and acceptability.

Other Method Name [*]

None

Comments

None

Method of Estimation (or Statistical Test of Hypothesis or Other Statistical Analysis required)

NA

Estimation Parameter [*]

NA

Other Parameter Name [*]

NA

Estimated Value [*]

NA

Confidence Interval (If applicable)

95%

Level [*]

NA

Number of Sides [*]

2-sided.

Lower Limit [*]

NA

Upper Limit [*]

NA

NA (Not Available) Explanation [*]

This is not relevant to our analysis

Parameter Dispersion Type

Standard Deviation

- Standard Error of the Mean

Dispersion Value

NA

Estimation Comments

NA

Other Statistical Analysis

NA

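### The outcome models use randomised women with at least one follow-up, not all enrollees, and the fallback for zero-inflated outcomes has no stated missing-data handling

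*Protocol*

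**What the plan says.** **Design.** The protocol (Methods - Randomized Pilot Trial) states: "Phase B will use a two-group, randomized, controlled design with 60 shelter residents". On outcome visits it adds: "There will be 3- and 6-month post-shelter computer-based follow up assessments".

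**Analysis set.** Protocol, Data Analysis, describes the primary analyses as intent-to-treat, "using data from all treatment enrollees". It contrasts them with a completer set defined by session attendance, not by follow-up.

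**Model.** Differences between conditions are explored with hierarchical linear models (HLM). The protocol adjusts for baseline, and the SAP (under Method) says the same: "Baseline values of each outcome variable will serve as a covariate in analyses".

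**Missing data.** The protocol says that HLM copes with missing data and is workable with 41 women. It also says: "We anticipate we will have complete data on approximately 41 participants". For an outcome too zero-inflated to transform, "it will be analyzed with logistic regression or generalized estimating equation techniques in this small pilot study". Nothing is said about missing data under that fallback. The check on missingness itself is: "We will compare rates of missing data across conditions". Neither document states a missing-data assumption, an imputation or weighting method, or a sensitivity analysis.

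**The concern.** With baseline as a covariate, the responses are the 3- and 6-month values only. A woman with neither has no outcome row and leaves the model, so the set described is not the set the model uses.

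The fallback is the weaker part. Likelihood-based HLM is valid when loss depends on observed data that are in the model (missing at random, MAR). Unweighted GEE in general is not, and plain logistic regression uses observed cases only. If women using at 3 months are less likely to return at 6 months, the observed 6-month rate is too low. Comparing how many are missing in each arm says nothing about who is missing.

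At stake are the arm-level rates and effect sizes that the protocol wants to use when planning a larger trial.

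**Working it through.** **1. The plan's figure of 41.** The Retention section gives 82% at 6 months, 80% at 9 months, and 85% or more in other treatment trials. 60 × 0.82 = 49.2; 60 × 0.80 = 48.0; 60 × 0.85 = 51.0. None gives 41. Products such as 60 × 0.85 × 0.80 = 40.8 come close, but the documents show no derivation. I take 41 as stated and do not call it wrong.

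**2. How many women could be left out.**
- Upper bound: a woman with no follow-up cannot have complete data, so at most 60 − 41 = 19 (32%).
- Lower bound: 0, if every incomplete case still has one visit.
- At 82% retention, with the same women missing both visits: 60 × 0.18 = 10.8, about 11.
- Direct check: in one simulated trial of 60 with 14 women lost to all follow-up, the baseline-as-covariate mixed model used 46.

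**3. Does the exclusion bias the adjusted arm difference?** The large-sample simulations below assume a correlation of 0.6 and a true 6-month effect of −0.40 SD. These values are not from the documents.

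| Loss depends on | HLM | GEE (independence) |
|---|---|---|
| nothing | −0.399 | −0.399 |
| baseline, in one arm | −0.401 | −0.401 |
| 3-month outcome, in one arm (6-month visit only) | −0.397 | −0.464 |
| unseen 6-month outcome, in one arm | −0.523 | −0.523 |

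Rows 1 and 2 show no bias from the exclusion. Row 3 separates HLM from GEE. In that row a logistic GEE gives a log odds ratio of −1.12 (independence) or −1.03 (exchangeable), against −0.93 or −0.94 with full data. In row 4 neither model helps.

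**4. Worked example for the fallback.** Assume 3-month use of 60% in control and 40% in SHE. The probability of 6-month use is 0.8 after 3-month use and 0.2 otherwise. The 6-month visit is missed by 45% of 3-month users and 15% of the rest. Overall loss is then 33% in control and 27% in SHE, close to the plan's 19/60.
- Control, true: 0.6 × 0.8 + 0.4 × 0.2 = 0.56. Observed: (0.6 × 0.55 × 0.8 + 0.4 × 0.85 × 0.2) / (0.6 × 0.55 + 0.4 × 0.85) = 0.332 / 0.67 = 0.496.
- SHE, true: 0.4 × 0.8 + 0.6 × 0.2 = 0.44. Observed: (0.4 × 0.55 × 0.8 + 0.6 × 0.85 × 0.2) / (0.4 × 0.55 + 0.6 × 0.85) = 0.278 / 0.73 = 0.381.
- Difference, same pattern in both arms: 0.496 − 0.381 = 0.115, against a true 0.12.
- Difference, pattern in SHE only: 0.56 − 0.381 = 0.179.

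These are observed-case rates, as given by logistic regression at 6 months or by GEE with an independence working correlation. Baseline is ignored for simplicity. Imputing 6-month use from 3-month use restores 0.56 and 0.44, because the link between the two visits is the same in women seen and not seen.

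**5. Why comparing rates is not enough.** Take the SHE-only pattern, and let control lose 27% for reasons unrelated to use. Both arms then lose 27%, the comparison shows nothing, and the difference is still off by 17.9 − 12 = 5.9 points.

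**6. Loss related to unseen outcomes.** The bias in the arm difference is p₁d₁ − p₀d₀, where p is the proportion lost and d is how much worse lost women are. With assumed losses of 42% and 22% (average 32%): d = 0.5 SD in both arms gives 0.21 − 0.11 = 0.10 SD; d = 1 SD gives 0.20 SD.

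**The case against.** **Status and scale.** Feasibility and acceptability are the primary goal, and the arm comparisons are exploratory. With about 20.5 women per arm the unadjusted 95% half-width is 1.96 × √(2/20.5) = 0.61 SD, or about 30 points for a proportion, so the shifts above are small beside sampling error. This stands, and it limits the importance of the point. The protocol also plans retention measures, telephone follow-up, and a look at why participants stopped. These may reduce loss or help describe it, but they do not supply an analysis for it.

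**The wording is loose, not wrong.** Intent-to-treat is set against a completer set based on sessions, so it may mean only that women are not removed for missing sessions. That is a fair reading, but the phrase still covers women whom the model cannot use.

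**Stronger readings that the documents do not support.**
- A reader might infer that the exclusion itself biases the arm comparison. Under MAR given arm and baseline it does not.
- A reader might infer a false claim that GEE handles missing data. The statement names HLM only, and is correct for women with one of two visits under MAR. For the fallback the fault is silence.
- A reader might set 41 against 60 as a contradiction. The 41 is an expected number with complete data and a remark on whether HLM is workable at that size. It does not define the analysis set.

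**A tempting remedy.** Modelling baseline as a repeated response would bring in all 60 women. In 1,000 simulated trials of 60, its estimates correlated 0.99 with the planned model's (mean SE 0.229 against 0.231), so the arm difference gains almost nothing. It also fits poorly here. Women with no baseline use or violence on the TLFB are excluded, so baseline is selected. The abuse-scale and using-days windows differ between sections. The covariance is to have few parameters. With compound symmetry, an assumed baseline SD 1.5 to 2 times the follow-up SD, and baseline-related loss in one arm, that model gave −0.34 to −0.33 against a true −0.40, while the planned model gave −0.40.

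**Conclusion.** The point holds in limited form. The HLM set is randomised women with at least one follow-up outcome, so the stated set is too broad by 0 to 19 of 60 women. The bounds follow from the plan's own 60 and 41. The figure of about 11 further assumes 82% retention and the same women missing both visits.

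The fallback is unprotected when 6-month loss depends on 3-month use. Arm-level rates then move by about 6 points in the example. The arm difference moves by 0.5 points if both arms share the pattern and by 5.9 points if only SHE has it. These sizes rest on assumed rates of use and loss; the direction does not depend on the exact values as long as users are lost more often and use persists between visits.

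No planned step shows how far results depend on loss related to unseen relapse. For an exploratory comparison in a pilot, the importance is low to moderate.

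**What to change.** 1. **Analysis set.** Define it as all randomised women, in their assigned arm, with at least one follow-up outcome. Report the number excluded by arm, and state that HLM assumes data missing at random.
2. **Fallback.** If an outcome goes to logistic regression or GEE, first multiply impute missing follow-ups from arm, baseline and 3-month data. Keep the imputation model small, given the sample size.
3. **Sensitivity analysis.** Prespecify one for outcome-related loss, for example setting missing follow-up using days to the woman's own 90-day pre-shelter TLFB level. Label it as one scenario, since it does not span the possibilities, and make sure the follow-up window it replaces is of the same length.

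Keep baseline as a covariate.

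Cost: no new data, a few more analysis runs, and slightly more complex reporting.
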